# **PROTOCOL SYNOPSIS**

Title	Robotic versus Electromagnetic Bronchoscopy for Pulmonary
	LesIon AssessmeNT)
Short title	RELIANT
Primary study objective	To compare the diagnostic yield of the Ion TM Endoluminal System (shape sensing catheter bronchoscopy, SSCB) to that of the ILLUMISITE TM Platform (electromagnetic navigational bronchoscopy, EMN) in patients undergoing bronchoscopy with planned biopsy of a peripheral pulmonary lesion.
Study devices	Ion TM Endoluminal System (SSCB); ILLUMISITE TM Platform (EMN).
Design	Single center, open label, pragmatic, non-inferiority, cluster randomized controlled trial.
Study centers	Vanderbilt University Medical Center
Number of clusters	N=202, to be increased if necessary
Inclusion criteria	
 
≥ 18 years of age at time of bronchoscopy.
 
Scheduled for navigational bronchoscopy for the evaluation of a peripheral pulmonary lesion.
 

Exclusion criteria	
 
Enrolled in a different study requiring use of one specific platform
 
Subject declines to participate.
 

Primary endpoint	
 
The primary endpoint will be diagnostic yield obtained from Ion™ or ILLUMISITE™ procedures, defined as the proportion of procedures that result in acquisition of lesional tissue. Lesional tissue: histopathological findings present that readily explain the presence of a pulmonary lesion.
 

Secondary endpoints	1. Duration of the procedure
Exploratory endpoints	
 
Need for additional diagnostic procedures
 
Radiation exposure
 
Diagnostic accuracy at 12-months post-biopsy
 

Safety outcome	
 
Rate of complications (including pneumothorax, bronchopulmonary hemorrhage, respiratory failure, anesthetic complications)
 

Subject follow-up	Patients without malignancy present on biopsy will be followed for up to 12 months as clinically required per standard of care.
Statistical methodology	We assume the diagnostic yield for EMN is 80%. The non-inferiority margin is set at 10%, cluster size of 2, and no intracluster correlation, we need 202 clusters (targeting 425 subjects to reach 202 per arm) to have an 80% power to conclude noninferiority at one-sided type I error rate set at 5%.
Interim analysis	There will be no interim analysis

#### **GENERAL STUDY INFORMATION**

Title: Navigation Robotic versus Electromagnetic Bronchoscopy for Pulmonary LesIon AssessmeNT (RELIANT)

Protocol Version Number and Date:

# STATEMENT OF COMPLIANCE

This human subject study will comply with all applicable federal, state, and local laws and regulations, including generally accepted standards of good clinical practice as adopted by current Food Drug Administration ("FDA") regulations and statutes. The study site shall only allow individuals who are appropriately trained and qualified to assist in the conduct of the study.

#### **BACKGROUND AND SIGNIFICANCE**

Peripheral pulmonary lesions (PPLs) are often biopsied to assess for the presence of infection, inflammation, or malignancy. Tissue can be acquired in a variety of ways: surgical resection, percutaneous transthoracic needle biopsy, or bronchoscopic biopsy. Bronchoscopy is commonly pursued to determine PPL etiology, with over 500,000 performed annually in the US alone. Advanced imaging and navigational guidance systems are required to accurately approach small peripheral lesions bronchoscopically (1, 2). A variety of navigational technologies are currently available, including electromagnetic navigational bronchoscopy (EMN), virtual bronchoscopy, thin and ultrathin bronchoscopes, and endobronchial ultrasound. No comparative data exist regarding the relative performance of these competing technologies, which are all considered standard of care and currently used interchangeably based on personal preferences and availability (2).

EMN platforms dominate the current navigational bronchoscopy market (2). The largest prospective multicenter study assessing EMN performance showed a diagnostic yield of 73% (3). The more recent addition of intraprocedural digital tomosynthesis has been reported to

increase EMN diagnostic yield to 75-83% (4-6); this feature is included in the ILLUMISITE™ electromagnetic navigational bronchoscopy platform (Medtronic, Minneapolis, MN, U.S.) and is labeled "fluoroscopic navigation".

Recently, the FDA cleared a novel navigational technology: shape-sensing catheter bronchoscopy (SSCB), via the 510(k) pathway (7, 8). This pathway requires a technical demonstration of safety and efficacy similar to that of an existing predicate device but does not usually require clinical data. Since market release in 2019, single-center prospective cohort data have emerged suggesting SSCB diagnostic yield is comparable to EMN (9), but no high-quality comparative data exist regarding the relative performance of these two technologies. Despite this important knowledge/data gap, SSCB has become a popular platform in the advanced bronchoscopist community. High-quality comparative data are required to inform optimal patient care. Additionally, EMN and SSCB platforms are considered capital purchases, each costing hundreds of thousands of dollars. Hence, it is also important for health care systems to have high quality data as they consider device purchases. VUMC currently utilizes both SSCB and EMN and they are used interchangeably in our two operating rooms. Patients are typically assigned arbitrarily to procedures using either platform based on operating room availability.

Thus, we propose a randomized controlled study to test the hypothesis that the diagnostic yield of SSCB is not inferior to EMN in patients undergoing bronchoscopy to biopsy a PPL.

# HYPOTHESIS AND STUDY OBJECTIVE(S)

#### **Hypothesis**

We hypothesize that the diagnostic yield of the Ion™ Endoluminal System (SSCB) is not inferior to the ILLUMISITE™ Platform (EMN) in patients undergoing bronchoscopy for biopsy of a PPL.

# **Objectives**

This is an investigator-initiated, non-inferiority, open labeled, cluster randomized controlled trial. Our primary objective is to compare the diagnostic yield of the IonTM Endoluminal System (SSCB) to the ILLUMISITETM Platform (EMN bronchoscopy) in patients undergoing bronchoscopy for PPL evaluation. Our secondary objective is to compare the rate of complications, procedure time, radiation exposure, absence of malignancy at 12 months, and need for additional procedures between these two bronchoscopic modalities.

#### **METHODS**

#### **General Study Design**

This is a single center, open label, pragmatic, non-inferiority, cluster randomized controlled trial. Patients with a PPL requiring navigational bronchoscopic sampling will be included. We have one EMN platform and one SSCB platform at VUMC. The platform set up in each of our two operating rooms will be randomly allocated each morning. Any navigational bronchoscopy scheduled in a given operating room that day will be performed with the platform allocated to that room on that day.

# **Study Population**

#### Inclusion Criteria:

- 1.  $\geq$  18 years of age at time of bronchoscopy.
- 2. Undergoing navigational bronchoscopy for biopsy of PPL

## Exclusion Criteria

- 1. Enrolled in a different study requiring use of one specific platform
- 2. Subject declines to participate

# Endpoints

# Primary Outcome

The primary endpoint will be diagnostic yield, defined as the proportion of procedures that results in acquisition of lesional tissue.

Lesional tissue is defined by the presence of pathological findings that readily explain the presence of a pulmonary lesion. The following common pathological findings are pre-specified:

- Malignancy
- Specific benign pathologic finding including
  - Organizing pneumonia
  - Frank purulence/robust neutrophilic inflammation
  - o Granulomatous inflammation
  - Other specific benign findings such as hamartoma, amyloidoma or other uncommon causes of PPLs with distinctive pathological patterns.

Biopsies not meeting any of the above lesional pathological criteria will be adjudicated as not meeting the primary outcome (not being "diagnostic"), including biopsies with normal lung parenchyma or airway components on biopsy, atypia not diagnostic of malignancy, or non-specific inflammation. A blinded panel will review all non-malignant biopsies at the end of accrual to confirm specific benign or non-diagnostic findings on biopsy. Procedures will be adjudicated as not meeting the primary outcome if the procedure starts but biopsies are not obtained (due to failure to navigate to the lesion, or complication, or equipment failure). A procedure will be considered started at induction of general anesthesia.

Biopsies obtained without the use of EMN or SSCB (e.g., sampling of central lymph nodes using the linear endobronchial ultrasound bronchoscope) will not be included in the diagnostic yield calculations. In case of repeat bronchoscopies, only the index bronchoscopy will be included in the diagnostic yield calculation.

# Secondary outcomes

1. Duration of procedure (in minutes), defined as time from the start of airway registration to the removal of the bronchoscope after completion of navigation procedures.

# Exploratory outcomes

- 1. Need for additional diagnostic procedures directed at the PPL of interest
- 2. Radiation exposure
- 3. Diagnostic accuracy at 12-months post-biopsy

# Safety outcome

1. Rate of procedure complications including respiratory failure, pneumothorax, anesthetic complications, and bronchopulmonary hemorrhage

# **Outcomes Definitions**

- *Rate of complications:* Number of procedures resulting in any complication divided by the total number of procedures.
- *Rate of specific complication:* Number of procedures resulting in a specific complication divided by the total number of procedures.
- *Need for additional diagnostic procedures:* Any diagnostic procedure performed after the study bronchoscopy which targets the same peripheral lesion (including repeat bronchoscopy, transthoracic needle biopsy, or surgical lung biopsy) will be considered an additional diagnostic procedure. Repeat biopsies of lesions determined to be malignant by study bronchoscopy which are 1) performed specifically to obtain additional tissue for further testing but that does not change the malignant diagnostic, or 2) therapeutic surgical resection of such lesions, will not be considered additional diagnostic procedures.
- *Radiation exposure:* Radiation dose delivered to the patient during the study bronchoscopy, recorded as a dose area product (mGy/cm2).
- *Diagnostic accuracy:* Number of true positive (malignant) lesions plus true negative (specific benign diagnosis) lesions with no evidence of malignancy at 12-month follow-up (no interval biopsy diagnostic of malignancy, regression on CT or stable size with no plan for repeat diagnostic procedure), divided by the total number of biopsied lesions.

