#### **Study Procedures**

Written research informed consent for the collection of data will be integrated within the clinical workflow when obtaining procedural consent (refer to Informed Consent section below) and all eligible patients will be enrolled. An allocation envelope will be opened by OR staff each morning to determine which room each platform will be set up in. The pre-operative steps and procedure will proceed per usual standard of care. Intubation and ventilation will follow our standard clinical protocol which is identical for both platforms (8.5 mm size endotracheal tube, a recruitment maneuver once the endotracheal tube is secured (PEEP of 40 cmH20 for 40 seconds), followed by ventilation with a PEEP of 15 cmH20 with as minimal FiO2 needed to maintain a SpO2 of >90%). The navigation procedures will be planned using pre-procedure CT scans of the chest and the planning software specific to each platform.

Bronchoscopy will be performed by interventional pulmonologists with expertise in navigational bronchoscopy and as per standard of care. Procedures will be performed under general anesthesia with neuromuscular blockade. Radial endobronchial ultrasound will be available for all procedures. Biopsies will be obtained using transbronchial needles, biopsy forceps, cytology brushes, cryoprobes, and/or other sampling devices at the discretion of the

bronchoscopist. Rapid on-site evaluation will be performed to assess for specimen adequacy. Additional biopsies obtained without the use of guided bronchoscopy (e.g., sampling of central lymph nodes using the linear endobronchial ultrasound bronchoscope) will be collected if clinically indicated but will be excluded from PPL diagnostic yield calculations. The procedure will be deemed non-diagnostic if the proceduralist is unable to reach the nodule (no biopsies obtained, representing navigation failure) or if a complication occurs before biopsies are obtained. All patients will recover based on our usual standard of care, which includes two hours of monitoring in the PACU before being discharged.

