inferiority margin set at 10%, cluster size of 2, and no intracluster correlation, we need 202 clusters (operating days) to have an 80% power to conclude noninferiority at a one-sided type I error rate of 5%, which corresponds to a target of 425 subjects to reach 202 per arm. The noninferiority margin has been chosen based on what would be considered a clinically significant difference (or, put differently, a difference which might influence a hospital to purchase one platform over the other). In case our average cluster size does not reach 2, we will plan to increase the number of clusters to meet our target enrollment of 425 subjects to reach 202 per arm.

Interventions

All patients meeting the eligibility criteria for this study will be enrolled. Cluster randomization will be used, and patients will be assigned to one of the two comparator arms:

a) IonTM Endoluminal System (SSCB)

b) ILLUMISITE[™] Platform (EMN)

Outcomes

Primary Outcome

The primary endpoint will be diagnostic yield, defined as the proportion of procedures that results in acquisition of lesional tissue.

Lesional tissue is defined by the presence of pathological findings that readily explain the presence of a pulmonary lesion. The following common pathological findings are pre-specified:

- Malignancy
- Specific benign pathologic finding including
 - Organizing pneumonia
 - Frank purulence/robust neutrophilic inflammation
 - o Granulomatous inflammation
 - Other specific benign findings such as hamartoma, amyloidoma or other uncommon causes of PPLs with distinctive pathological patterns.

Biopsies not meeting any of the above lesional pathological criteria will be adjudicated as not meeting the primary outcome (not being "diagnostic"), including biopsies with normal lung parenchyma or airway components on biopsy, atypia not diagnostic of malignancy, or non-specific inflammation. A blinded panel will review all non-malignant biopsies at the end of accrual to confirm specific benign or non-diagnostic findings on biopsy. Procedures will be adjudicated as not meeting the primary outcome if the procedure starts but biopsies are not obtained (due to failure to navigate to the lesion, or complication, or equipment failure). A procedure will be considered started at induction of general anesthesia.

Statistical analysis plan for Robotic versus Electromagnetic Bronchoscopy for Pulmonary LesIon AssessmeNT: the RELIANT trial PI: [name]

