Biopsies obtained without the use of EMN or SSCB (e.g., sampling of central lymph nodes using the linear endobronchial ultrasound bronchoscope) will not be included in the diagnostic yield calculations. In case of repeat bronchoscopies, only the index bronchoscopy will be included in the diagnostic yield calculation.

Secondary Outcomes

There is one secondary outcome for the trial, which will be collected during the bronchoscopy procedure.

a) Duration of procedure (in minutes), defined as time from the start of airway registration to

the removal of the bronchoscope after completion of navigation procedures.

Exploratory Endpoint(s)

There are three exploratory endpoints that are prespecified. These can be collected during and immediately after the bronchoscopy procedure, and/or during the follow-up period.

a) Need for additional diagnostic procedures. Any diagnostic procedure performed within 12 months of the study bronchoscopy that targets the same peripheral lesion (including repeat bronchoscopy, transthoracic needle biopsy, or surgical lung biopsy) will be considered an additional diagnostic procedure.

1. Repeat biopsies of lesions determined to be malignant by study bronchoscopy which are 1) performed specifically to obtain additional tissue for further testing but that does not change the malignant diagnosis, or 2) therapeutic surgical resection of such lesions, will not be considered additional diagnostic procedures.

b) Radiation exposure, defined as radiation dose delivered to the patient during the study bronchoscopy, recorded as a dose area product (mGy/cm2).

Diagnostic accuracy

Diagnostic accuracy will be assessed for the two devices. Lesions will be categorized as positive (malignant) lesions or negative (specific benign diagnosis). The criterion standard for a negative diagnosis will be no evidence of malignancy at 12-month follow-up (no interval biopsy diagnostic of malignancy, regression on CT or stable size with no plan for repeat diagnostic procedure).

Safety outcome

The main safety outcome for this trial is occurrence of procedure complication(s), defined as the occurrence of any of the following: respiratory failure, pneumothorax, anesthetic complications, and bronchopulmonary hemorrhage.

Safety outcomes will be reported overall and by type.

Statistical analysis plan for **R**obotic versus Electromagnetic Bronchoscopy for Pulmonary LesIon Assessme**NT**: the RELIANT trial PI: [name]

Analysis dataset

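### Twelve-month diagnostic accuracy leaves out started procedures with no biopsy, which flatters whichever platform has more of them

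*Protocol*

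**What the plan says.** Protocol, Exploratory outcomes, lists "Diagnostic accuracy at 12-months post-biopsy" third of three. Protocol, Outcomes Definitions, gives its numerator as "Number of true positive (malignant) lesions plus true negative (specific benign diagnosis) lesions with no evidence of malignancy at 12-month follow-up" and its denominator with the words "divided by the total number of biopsied lesions". In the same list, the complication rates are "divided by the total number of procedures".

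The primary endpoint treats procedures without a biopsy differently. Protocol, Primary Outcome: "Procedures will be adjudicated as not meeting the primary outcome if the procedure starts but biopsies are not obtained". The SAP's primary outcome repeats the rule. Protocol, Study Procedures, also calls a procedure non-diagnostic when the operator is "unable to reach the nodule (no biopsies obtained, representing navigation failure", or when a complication comes before any biopsy.

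The SAP gives accuracy no denominator. Its outcome definition says "Lesions will be categorized as positive (malignant) lesions or negative (specific benign diagnosis", which has no place for a lesion without a biopsy or with a non-diagnostic one. Its later Diagnostic accuracy section lists sensitivity, specificity, predictive values and likelihood ratios by device. Its Analysis dataset section sets an intent-to-treat approach covering all eligible participants, and Secondary and exploratory analysis says that exploratory endpoints are handled much as the primary is. Missing exploratory outcomes get a complete-case analysis.

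**The concern.** Whether a biopsy is obtained depends on the platform. The causes that the plan names for no biopsy are failed navigation, a complication and equipment failure, and all three arise after allocation. Restricting accuracy to biopsied lesions conditions the comparison between arms on a result of the device under test.

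The measure is also uneven in what it counts. A lesion that is sampled without a diagnosis stays in the denominator and counts against the platform. A lesion that is never sampled disappears. The operator is unblinded, so setting aside a difficult lesion costs the platform nothing on this measure, while sampling it and missing does.

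At stake is how the 12-month result is read. The background section says that the trial should inform device purchases. An accuracy figure showing parity could hide a difference in how often each platform obtains tissue at all.

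**Working it through.** **Inputs from the documents.** The numerator and denominator of accuracy (Protocol, Outcomes Definitions); the rule for procedures without a biopsy (Protocol and SAP, primary outcome); the design figures of 80% yield in both arms, a 10% margin, one-sided alpha 5%, 202 per arm and no intracluster correlation (Protocol, Sample Size Calculation). The documents give no expected accuracy and no no-biopsy rate, so every value of these below is an assumption.

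**The plan's own figure.** The Farrington-Manning test with D0 = -0.10 has restricted proportions 0.7411 and 0.8411.
- Null standard error: sqrt((0.7411 x 0.2589 + 0.8411 x 0.1589)/202) = 0.04015.
- Alternative standard error: sqrt(2 x 0.8 x 0.2/202) = 0.03980.
- Power: Phi((0.10 - 1.645 x 0.04015)/0.03980) = 0.803, against 0.80327 in the Protocol's table.

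This figure concerns diagnostic yield and does not involve accuracy.

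**Relation between the two denominators.** Take one lesion per procedure. Let f be the share of started procedures with no biopsy. Then

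accuracy per biopsied lesion = accuracy per started procedure / (1 - f).

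The factor 1/(1 - f) is 1.020 at f = 2%, 1.111 at 10% and 1.176 at 15%. It rises with f, so the platform with more no-biopsy procedures always gets the larger factor.

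**Illustration per 100 started procedures (assumed).**

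| | Platform A | Platform B |
|---|---|---|
| No biopsy | 2 | 10 |
| Accurate | 79 | 72 |
| Per started procedure | 79/100 = 79.0% | 72/100 = 72.0% |
| Per biopsied lesion | 79/98 = 80.6% | 72/90 = 80.0% |

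The gap goes from 7 points to 0.6. B is flattered but still ranks second.

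**Range when failures are random and accuracy a per biopsied lesion is equal.** The Protocol's measure shows no difference. The gap per started procedure is a x (fB - fA):
- a = 80%, 2% v 4%: 0.80 x 0.02 = 1.6 points
- a = 70%, 2% v 5%: 0.70 x 0.03 = 2.1 points
- a = 75%, 2% v 10%: 0.75 x 0.08 = 6.0 points (73.5% v 67.5%)
- a = 80%, 5% v 15%: 0.80 x 0.10 = 8.0 points

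**When the ranking reverses.** Suppose 25% of lesions are hard, with accuracy if biopsied of 50% for hard and 85% for easy lesions. A biopsies every lesion. B leaves 40% of hard lesions unbiopsied, so f = 0.25 x 0.40 = 10%.
- A: 0.75 x 0.85 + 0.25 x 0.50 = 76.3% on either denominator.
- B: 0.75 x 0.85 + 0.15 x 0.50 = 71.3% per started procedure, and 0.7125/0.90 = 79.2% per biopsied lesion.

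B trails by 5 points on one denominator and leads by 2.9 on the other. More generally, at 2% v 10% with A at 75% per biopsied lesion, the ranking reverses only if B's figure per biopsied lesion lies between 75% and 0.75 x 0.98/0.90 = 81.7%.

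**The case against.** The strongest reply is that this is a choice of estimand. The endpoint's name presupposes a biopsy: it asks whether the result was right, and yield already covers failure to get one. Sensitivity and specificity likewise need a test result. Counting every started procedure would also make accuracy close to yield less the benign diagnoses not upheld at 12 months, which is nearly redundant with the primary endpoint.

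This does not settle the matter. A measure of whether results are right would also set non-diagnostic biopsies aside, and the Protocol's keeps them as failures. It is a success rate that counts one kind of platform failure and drops another. The redundancy argument applies equally to the present version, which has the same numerator divided by a smaller number.

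Much else in the defence stands. The endpoint is exploratory, with no decision or power calculation resting on it. Yield counts the failures, and need for additional diagnostic procedures captures those followed by another biopsy. A small imbalance hides little, and even the 7-point gap is imprecise: with 202 per arm and no clustering, its 95% interval is 7 ± 1.96 x sqrt((0.79 x 0.21 + 0.72 x 0.28)/202) = -1.4 to 15.4 points.

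A reader might also infer that patients with several sampled lesions will be counted several times. The denominator's wording leaves this open, but the documents otherwise speak of one target lesion and nowhere describe sampling several.

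**Conclusion.** The concern holds as a weakness of an exploratory endpoint that should be corrected. The denominator in Outcomes Definitions removes started procedures with no biopsy, no other section restores them, and the SAP's intent-to-treat statement is not reconciled with this. Accuracy is raised by 1/(1 - f), and more so for the platform with the larger f. The size depends on assumed values: about 2 to 8 points hidden across most of the range shown, and less when the two no-biopsy rates are close.

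Three stronger readings are not supported:
- **That the platform failing more often will come out ahead.** In the main illustration it does not. A reversal needs failures concentrated in hard lesions or a modest advantage among biopsied lesions.
- **That the trial's conclusion is affected.** The primary endpoint counts these failures, so the non-inferiority test and the sample size are untouched.
- **That accuracy is there to confirm the yield result.** Neither document gives it that role.

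**What to change.** 1. In Protocol, Outcomes Definitions, define accuracy per started index procedure, by assigned arm, on the target lesion planned before the procedure, with no biopsy counted as not accurate.
2. Add that denominator to the SAP's accuracy definition and to its later Diagnostic accuracy section; neither states one now. Say that no biopsy is a known outcome and not a missing value; otherwise the complete-case rule could remove these procedures again.
3. Use one definition of a started procedure. The primary outcome in both documents dates it from induction of anesthesia, while the SAP's Analysis dataset section requires navigation itself to have begun. Complications or equipment failures between those points are in or out depending on the section.
4. Keep the figure per biopsied lesion as a descriptive result, with the number of no-biopsy procedures in each arm beside it.

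The cost is a short amendment to each document, plus agreement on the starting point. No new data are needed, because the primary endpoint already requires no-biopsy procedures to be identified. Reported accuracy will be slightly lower in both arms.
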